### **13.3. Primary endpoint definition**

Failure-free survival (FFS), defined by the time from randomisation to first biochemical failure, recommencement of androgen deprivation therapy, local recurrence, lymph node/pelvic recurrence, distant metastases or death due to prostate cancer.

Biochemical (PSA) failure is defined following the RTOG-ASTRO Phoenix Consensus definition: an increase in serum PSA  $\geq 2$ ng/ml greater than the post-treatment nadir.

In addition, it is recognised that after high dose radiotherapy a benign PSA bounce is seen in up to 20% of patients, usually within the first 2 years. In some cases the magnitude of the bounce is high enough for the patient to be incorrectly classified as a PSA failure. To prevent this, PSA failure before 24 months will require 3 consecutive rises in PSA (not less than 6 weeks apart) resulting in a clinical diagnosis of failure, or commencement of further treatment (e.g. ADT). After 24 months, the definition of PSA failure for patients receiving radiotherapy will revert to the Phoenix definition described above (i.e. nadir+2 ng/ml).

### **13.4. Secondary endpoint definitions**

- Time to loco-regional recurrence (local or lymph node/pelvic recurrence) measured from randomisation; recurrence will be confirmed by radiological evaluation and/or pathological

confirmation.

- Time to biochemical or clinical failure, defined by the time from randomisation to first biochemical failure, recommencement of androgen deprivation therapy, local recurrence, lymph node/pelvic recurrence or distant metastases, measured from randomisation.
- Metastatic relapse free survival (time from randomisation to distant metastases or prostate cancer death); distant metastases will be confirmed by radiological evaluation and/or pathological confirmation. Site of distant recurrences will be recorded.
- Overall survival; this will include deaths from any cause. Time will be measured from randomisation.
- Prostate cancer specific survival; this will include deaths from prostate cancer only. In general, patients with death recorded as prostate cancer related with no prior recurrence of the disease will be reviewed on a case by case basis. Patients with an unknown cause of death will be assumed to have died from prostate cancer if they have a previously reported progression, otherwise they will be assumed to have died from other causes. Patients dying from other causes will be censored at date of death. Time will be measured from randomisation.
- Time to recommencement of androgen deprivation therapy; date on which anti-androgens or LHRH analogues/antagonists are started or date on which orchidectomy occurs.
- Acute bladder and bowel toxicity at 18 weeks; will be measured using the RTOG and NCI CTCAE scoring systems.
- Acute and late toxicity; will be measured using the RTOG and NCI CTCAE scoring systems.
- Quality of life endpoints (see section 20).
- Health economic endpoints (see section 20).

### **13.5. Exploratory endpoints**

We will record the number of patients with boost volumes on staging fMRI scans, and if the patient is not included in the focal boost randomisation (patient related, tumour / imaging characteristics, resources and availability). The data will help to evaluate the benefit and rule of staging with functional MRI imaging.

### **13.6. Analysis plan**

The principal analysis will occur after a median follow-up of five years or the target numbers of events have been reached, whichever occurs first. A total of 820 events (217 events x 2 (A, B) + 193 events x 2 (C, D)) to detect a difference of 7% with 85% (A vs B) or 80% (A vs C, D) power is required. Should the analysis not be event driven, the timing will be subject to approval from the IDMC.

The primary comparisons will compare each of the experimental arms to the standard (i.e. A vs B, A vs C and A vs D) and will include all randomised patients (intention-to-treat analysis). Only contemporaneously randomised controls will be used for the A vs C and A vs D comparisons. As secondary analyses, comparisons between experimental arms will also be reported, as well as the overall impact of prostate IMRT vs prostate and pelvis IMRT (A+C vs B+D) and no prostate boost vs prostate boost (A+B vs C+D). Exploratory analysis of the heterogeneity of treatment effect across whole gland or focal boosts, and type of focal boost (IMRT or HDR) will be performed.

All treatment effects will be presented with 2-sided 95% confidence intervals. Adjustment will be made for multiple testing as appropriate. Time to event endpoints will be summarised presenting estimated Kaplan-Meier curves (by treatment); the time point of primary interest is 5 years from randomisation, which will be presented with 95% CI for each treatment arm. Treatment effects will be estimated and tested for significance by the Cox proportional hazards model, adjusting by stratification factors.

Adjusted models will include the duration of ADT prior to starting radiotherapy (as a result of COVID19 related delays to radiotherapy starting). Further models adjusting by other important known prognostic factors will also be fitted. Methods to account for non-proportionality will be used if appropriate. Acute and late side effects will be summarised as frequencies and percentages at each time point. Acute toxicity will also be summarised as worst toxicity reported during radiotherapy. The proportion experiencing grade $\geq$ 2 side effects will be presented; comparisons between treatment groups will be tested using chi-squared or Fishers exact tests. Logistic regression models will be used to estimate treatment differences (odds ratios). Analysis of QL and health economic endpoints are further detailed in Section 20.

Further details of analysis methods will be specified in a Statistical Analysis Plan in accordance with ICR-CTSU Standard Operating Procedures. The Statistical Analysis Plan will include a section to detail how data impacted by strategies introduced to mitigate risks relating to the COVID19 pandemic will be handled.

Any quality of life data collected from PIVOTALboost participants within the SPRUCE study will be shared with PIVOTALboost for analysis.

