#### Updated sample size calculation:

Recruitment to the 4 arm randomisation was slower than expected and the switch to 1:1:1:1 was not made. This has meant that the sharing of arm A patients for the B comparisons compared to the C and D comparisons is less than expected (from assumed 90% (459:517) it is around 20% (144 shared A's out of 763) by February 2022). This means that recruitment into A vs C vs D needs to continue beyond arm B completing target recruitment.

The sample size for A vs C and A vs D has been revisited under this scenario, keeping the same sample size assumptions, but allowing for the fact that recruitment would not be complete in 4.5 years. With the recruitment period extended by 2 years to 6.5 years and the pattern of staggered recruitment to date used the following is true:

- to achieve 80% power to detect a HR of 0.624 (translating to a 7% difference in 5 year FFS between A and C (or A vs. D), assuming 5 year event free rate of 80% in arm) and retaining a conservative alpha of 0.017, 192 events are required (under 1:1 allocation). This number of events would be observed if 847 patients, (822 plus 3% for loss to follow-up) are recruited over 6.5 years and followed up for 5 years. The overall sample size for A vs C (A vs D) remains the same when the allocation ratio A:C (A:D) is 2:3 or 1:1.

Once arm B has completed target recruitment, the trial will recruit patients to arms A, C and D in the ratio 1:1:1. Recruitment will be complete when 847 patients have been randomised to Arms A and C and 847 patients have been randomised to Arms A and D. Overall, the total recruitment across all four arms will be 2195 (see appendix 4, for details based on recruitment up to Feb 2022).

The sample size calculation is based on the log-rank test using the 'artsurv' command in STATA, incorporating 4.5 years of staggered recruitment and a minimum of 5 years of follow-up.

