**Stata code for sample size:**

```
artsurv, method(l) nperiod(23) ngroups(2) fp(0) edf0(0.8, 10) hratio(1, 0.624) ///  
alpha(0.017) power(0.8) aratios(1 1 ) recrt(13 0, 0.034 0.051 0.059 0.048 0.027 0.038  
0.044 0.089 0.122 0.122 0.122 0.122 0.122 , 0 ) ///  
distant(0) detail(0) onesided(0) ni(0) tunit(2) trend(0)
```

Note: the Stata code uses 1:1 ratio, however the actual ratio at the end will be somewhere between 2:3 (the ratio used for the 4-arm randomisation) and 1:1 (the ratio used for the 3-arm randomisation). Using 1:1 and 2:3 results in a different number of events required but the same number of patients to reach that number of events so has no impact on the actual sample size, therefore 1:1 has been used for simplicity.

This protocol is a controlled document and should not be copied, distributed or reproduced without the written permission of the ICR-CTSU

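### Section 13.6 permits the principal analysis at a median of five years' follow-up, but the 80% power for A vs C and A vs D assumes a minimum of five years; at the median it is about 65-67%

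*Protocol*

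**What the plan says.** Section 13.6 sets the time of the principal analysis: "The principal analysis will occur after a median follow-up of five years or the target numbers of events have been reached, whichever occurs first". It then quotes target events with 85% power for A vs B and 80% for A vs C and A vs D, and adds: "Should the analysis not be event driven, the timing will be subject to approval from the IDMC". It does not say over which patients the median is taken.

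Section 13.1, under the updated sample size, sets out what is needed "to achieve 80% power to detect a HR of 0.624" at a two-sided alpha of 0.017. The requirement is 192 events under 1:1 allocation, which are expected if 847 patients (822 after 3% loss) "are recruited over 6.5 years and followed up for 5 years". The closing sentence of that section describes the calculation as "incorporating 4.5 years of staggered recruitment and a minimum of 5 years of follow-up". Its 4.5 years is out of step with the 6.5 years above it, but the five-year minimum agrees.

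The Stata code in Appendix 4 settles the timing that was used: "nperiod(23) ngroups(2) fp(0) edf0(0.8, 10"), with two periods per year. That is 13 half-years of accrual plus 10 of follow-up.

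**The concern.** A median of five years and a minimum of five years are different dates, and with back-loaded accrual they lie far apart. The event target and power in section 13.1 belong to the minimum. Section 13.6 permits analysis at the median and still quotes 80% power.

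Two of the three primary comparisons are affected. The protocol extended recruitment by two years and raised the total to 2195 in order to keep 80% power for them. If the median condition is acted on, part of what that extension bought is given up, and a true hazard ratio of 0.624 would be missed about one time in three instead of one in five.

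**Working it through.** **Inputs, all from the protocol.** Control failure-free survival is 80% at five years (13.1). The hazard ratio is 0.624, two-sided alpha 0.017 and evaluable patients 822 (13.1). Accrual weights per half-year are 0.034, 0.051, 0.059, 0.048, 0.027, 0.038, 0.044, 0.089, then five of 0.122 (Appendix 4 code). Entry is taken as uniform within each half-year and failure times as exponential.

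**Hazards.** Control: −ln(0.80)/5 = 0.04463 per year. Experimental: 0.624 × 0.04463 = 0.02785 per year, so five-year survival is exp(−5 × 0.02785) = 87%, as the plan states.

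**Formulas.** Expected events in an arm at time T are the arm size times the accrual-weighted average of 1 − exp(−hazard × (T − entry time)). Power is computed in two ways, with z = 2.387 for alpha 0.017 and |ln 0.624| = 0.4716:
- Schoenfeld: Φ(√(d·p(1−p)) × 0.4716 − 2.387), where d is total events and p the experimental share of patients.
- Arm-specific variance: Φ(0.4716/√(1/d0 + 1/d1) − 2.387).

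**Reproducing the plan, T = 11.5 years, 1:1.** Events are 411 × 0.2807 = 115.4 and 411 × 0.1864 = 76.6, total 192.0. Schoenfeld: √(192 × 0.25) × 0.4716 − 2.387 = 0.880, power 81%. Arm-specific: 0.4716/0.1474 − 2.387 = 0.813, power 79%. These match the stated 192 events and 80%.

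**When the median reaches five years.** The first eight weights sum to 0.39, so 61% of accrual falls in the last 2.5 years. Median entry is 4 + 0.5 × (0.50 − 0.39)/0.122 = 4.45 years. Median follow-up within the comparison is therefore five years at 9.45 years, when the last patient has 9.45 − 6.5 = 2.95 years. At 11.5 years the median would be 11.5 − 4.45 = 7.05 years.

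**Power at 9.45 years, 1:1.** Events are 411 × 0.2118 = 87.0 and 411 × 0.1386 = 57.0, total 144.0. Schoenfeld: √(144 × 0.25) × 0.4716 − 2.387 = 0.443, power 67%. Arm-specific: 0.4716/0.1704 − 2.387 = 0.381, power 65%. With no allowance for loss (847 patients) there are 148 events and Schoenfeld power is 69%.

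**At 2:3.** Events are 69.6 + 68.4 = 138.0. Schoenfeld: √(138 × 0.24) × 0.4716 − 2.387 = 0.327, power 63%.

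**Would the event condition act first?** No, under the design assumptions. The 192 events arrive at about 11.5 years, two years after the within-comparison median. The total of 820 in 13.6 is more distant still. Suppose all 2196 patients of Appendix 4 (A 763, B 517, C 458, D 458) had entered on day zero and every experimental arm had hazard ratio 0.624. By 11.5 years that gives 763 × 0.401 + 1433 × 0.274, or about 700 events.

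**Median over the whole trial (assumption needed).** The protocol does not give accrual by period for the other arms. The 1098th of 2196 patients is the median.
- If the 1458 patients of the Appendix 4 table accrued in the A vs C pattern, that entry corresponds to 1098/1458 × 356 = 268 on the A vs C count. The first seven half-years hold 246 and the eighth 73, so median entry is 3.5 + 0.5 × 22/73 = 3.65 years. Analysis at 8.65 years gives about 124 events and 57-60% power.
- If those 1458 accrued evenly to April 2022 (4.25 years), median entry is 1098/1458 × 4.25 = 3.20 years. Analysis at 8.2 years gives about 113 events and about 55% by Schoenfeld.

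**The case against.** The best reply is that the early date is not automatic. An analysis that is not event driven needs IDMC approval, and the IDMC reviews efficacy data at least annually (13.7), so it would see a shortfall and could wait. That stands as a partial safeguard: the loss of power is conditional on the median date being used. It is not a full answer, because the clause sets no minimum number of events or follow-up and does not say that power would be lower. The IDMC could properly approve the very date the protocol names.

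It can also be said that the SAP may define the population for the median. It may, but the conflict remains on the most favourable reading, with the median taken within the comparison.

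Three stronger readings are tempting and are not supported:
- A reader might infer that the boost comparisons simply have 55-60% power. That needs a whole-trial median, which 13.6 does not specify, and an assumed accrual curve.
- A reader might put the 84.4% control rate cited in 13.1 into the same calculation and obtain lower figures. The plan deliberately uses 80%. At 84.4% even the full 11.5-year design gives only about 151 events and 70% power, so much of that fall comes from the control rate and not from the trigger.
- A reader might treat the patients with less than five years of follow-up as a separate flaw. Kaplan-Meier and Cox methods handle that censoring, and the cost in precision is already in the event count.

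**Conclusion.** The inconsistency is real and the protocol is wrong as written: the trigger in 13.6 does not deliver the power quoted beside it. With the median taken within the comparison, about 144 of 192 events (75%) are expected and power is 65-67% at 1:1, so the type II error is about 33-35% where 20% is stated. At 2:3 power is about 63% by Schoenfeld; the full 11.5-year design at 2:3 gives 184 events and 77% by the same formula, so the trigger accounts for most but not all of that gap from 80%. These figures rest only on protocol inputs and exponential failure times. The whole-trial reading, at about 55-60%, is indicative because it depends on an accrual pattern the protocol does not give. All of this applies if the analysis takes place when the median condition is met. A vs B is not assessed here.

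**What to change.** For A vs C and A vs D, replace the median condition in 13.6 with the comparison's own event target or a minimum of five years of follow-up for every patient in that comparison, as the sample size assumes. Use 192 events, since 13.6 still carries the 193 of the initial calculation, and correct the 4.5 years in the last sentence of 13.1 to 6.5.

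If the sponsor prefers to keep a median rule, state which patients the median covers and restate the power at that time as about 65-67% for a within-comparison median at 1:1.

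The cost is wording only, with no added patients or assessments. The readout of the boost comparisons comes about two years later than under the median rule (11.5 − 9.45 = 2.05 years), at the date the sample size already assumes. Whether A vs B is reported earlier is for the sponsor to decide; 144 of its arm A patients are also controls for the boost comparisons (Appendix 4). The change should be made before any unblinded analysis of the primary endpoint, so that the date is not chosen with knowledge of the results.

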## 10. TREATMENT

### 10.1. Randomisation options

Patients will be eligible for entry into one of the following randomisation options according to:

- boost volume (whether the tumour volume identified on the staging MRI is suitable for focal boost or not),
- suitability and availability of HDR (e.g. patient not suitable for HDR brachytherapy or any other clinical reason) and,
- type of focal boost (IMRT or HDR brachytherapy).
- Suitability and availability of focal IMRT boost.

In centres with no access to HDR or focal IMRT boost, all patients will enter randomisation option 1 (irrespective of having a suitable boost or not). Randomisation option 1 closed to recruitment on 1st April 2022

**Randomisation Option 1 (Pelvic node randomisation):** No suitable focal boost volume on the staging MRI\* and not suitable for HDR brachytherapy:

Arm	Radiotherapy treatment area	
	Prostate dose	Pelvic node dose
A	60Gy/20#	
B	60Gy/20#	47Gy/20#

*\*this includes patients with post-biopsy MRI and patients with pre-biopsy MRI not fulfilling conditions for suitable boost*

**Randomisation Option 2a (Pelvic node and whole gland boost):** No suitable focal boost volume on the staging MRI\* and suitable for HDR:

Arm	Radiotherapy treatment area		
	Prostate dose	Pelvic node dose	Whole gland HDR
A	60Gy/20#		
B**	60Gy/20#	47Gy/20#	
C1	37.5Gy/15#		15Gy/1#
D1	42Gy/20#	47Gy/20#	15Gy/1#

*\*this includes patients with post-biopsy MRI and patients with pre-biopsy MRI not fulfilling conditions for suitable boost.*

*\*this also includes patients who have a suitable boost volume on MRI at a HDR centre where only **whole gland HDR** is RTQA is approved.*

*\*\*Arm B closed to recruitment in Q2 2022*

**Randomisation Option 2b (Pelvic node and focal boost randomisation):** Suitable focal boost volume

[figure not shown]
Arm	Radiotherapy treatment area			
	Prostate dose	Pelvic node dose	Focal Boost dose	
			Focal IMRT**	Focal HDR**
A	60Gy/20#			
B***	60Gy/20#	47Gy/20#		
C2	60Gy/20#		67Gy/20#	
C2	37.5Gy/15#			15Gy/1# (whole prostate) 19Gy/1# (tumour boost dose)
D2	60Gy/20#	47Gy/20#	67Gy/20#	
D2	42Gy/20#	47Gy/20#		15Gy/1# (whole prostate) 19Gy/1# (tumour boost dose)

*\*\* use of focal HDR or focal boost IMRT determined for each patient prior to randomisation.*

See figure 1 (next page) for the decision algorithm to determine what randomisation option corresponds to each patient.

*\*\*\* Arm B closed to recruitment in Q2 2022*

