#### Initial sample size calculation:

The study was powered to detect a 7% difference in 5-year FFS for each experimental arm compared to A (B, C or D) from 80% to 87%. This difference corresponds to a hazard ratio (HR) of 0.624 for each experimental arm as compared to A. This HR was chosen as sufficient to warrant a change in practice in the knowledge that more extreme effects have been reported in similar settings e.g. HR=0.47 in the ASCENDE trial [65]. In order to adjust for multiplicity [66] the 2-sided significance level for each comparison is set to 0.017 (0.05/3). As it was acknowledged that it could be easier to recruit more patients in the A vs. B comparison (see section 13.2 below), we allowed for more patients in the A vs. B comparison:

- to achieve 85% power to detect a 7% difference in 5 year FFS between A and B, 517 patients per group are needed (502 per group to observe 217 events, plus 3% for loss to follow-up).
- to achieve 80% power to detect a 7% difference in 5 year FFS between A and C (or A vs. D), a total of 918 patients are needed (a total of 892 to observe 193 events, plus 3% for loss to follow-up). The overall sample size for A vs C (A vs D) remains the same when the allocation ratio A:C (A:D) is 2:3 or 1:1.

Treatment allocation will be by minimisation. For the 2 way randomisation (A vs B) the ratio will be 1:1. Treatment allocation in the 4 arm randomisation was based on using a 2:2:3:3 ratio initially as it was expected fewer sites will be able to offer boost treatment groups (C and D). The plan was to closely monitor recruitment and adjust the allocation ratio in the 4 arm randomisation to 1:1:1:1 to ensure 9:9:8:8 (517:517:459:459) final relative numbers. The overall sample size was therefore **1952** patients.

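### Section 13.6 applies the concurrent-control rule to A vs C and A vs D but not to A vs B, so read literally A vs B takes in arm A patients randomised after arm B closed

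*Protocol*

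**What the plan says.** Section 13.6 says that the primary comparisons (A vs B, A vs C, A vs D) "will include all randomised patients (intention-to-treat analysis"). The next sentence restricts the control group: "Only contemporaneously randomised controls will be used for the A vs C and A vs D comparisons". No such restriction is given for A vs B. Treatment effects come from a Cox model adjusted for the stratification factors. Section 13.2 lists these as centre, NCCN risk group and suitability for focal boost, plus type of boost for Options 2a/2b.

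Section 13.1 describes recruitment after arm B: "Once arm B has completed target recruitment, the trial will recruit patients to arms A, C and D in the ratio 1:1:1". Sections 7 and 10.1 date the closure of arm B to Q2 2022 and of Option 1 to 1 April 2022. Section 13.1 gives the overlap between the comparisons as "144 shared A's out of 763".

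On who could receive what, section 3 says that allocation is made within each randomisation option. Section 10.1 says "In centres with no access to HDR or focal IMRT boost, all patients will enter randomisation option 1". Option 1 also takes patients with no suitable focal boost volume who are not suitable for HDR. Option 1 patients could be allocated only to A or B.

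**The concern.** An A vs B hazard ratio is protected by randomisation only for patients who could have gone to either arm. Section 13.6 states a concurrent-control rule for two of its three comparisons and leaves the third under all randomised patients. That third comparison is the one whose experimental arm closed while the control arm stayed open. An analyst who follows the text as written would add later arm A patients to A vs B. Those patients differ from the arm B patients in calendar period and in option mix, and the comparison would still be labelled intention-to-treat.

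There is a related but smaller gap. The word contemporaneously describes time, not eligibility. Option 1 arm A patients were randomised during the same years as C and D but could not have been allocated to either, and section 13.6 does not say in words that they are left out of A vs C and A vs D.

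**Working it through.** **The plan's own sizing for A vs C (A vs D).** Inputs from section 13.1: "the 2-sided significance level for each comparison is set to 0.017 (0.05/3"), "to achieve 80% power to detect a HR of 0.624", and "retaining a conservative alpha of 0.017, 192 events are required (under 1:1 allocation").

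- Schoenfeld: 4(z₁₋α/₂ + z₁₋β)² / (ln HR)² = 4 × (2.387 + 0.842)² / (ln 0.624)² = 188 events, rounded up.
- Freedman: (z₁₋α/₂ + z₁₋β)² × [(1 + HR)/(1 − HR)]² = 195 events, rounded up.
- The stated 192 lies between the two.
- With exponential FFS (80% at 5 years in A), the half-yearly accrual weights in Appendix 4 and analysis at 11.5 years, the event probabilities are 0.281 (A) and 0.186 (C). Then 192 / [(0.281 + 0.186)/2] = 822 patients, and 822 × 1.03 = 847. The stated figure is reproduced.

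**Which arm A patients the sizing counts.** These are the arm-level cells of Appendix 4, estimated from recruitment to February 2022 and assuming that arm B completes. The printed option totals, 724 and 674, do not equal their columns (373 + 371 = 744; 144 + 146 + 212 + 212 = 714), but the overall 1458 does, so the cells are used.

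| Arm A patients | n | Could have been allocated to |
|---|---|---|
| Option 1 | 373 | B |
| Option 2, while B was open | 144 | B, C, D |
| Option 2, after B closed | 246 | C, D |
| Total | 763 | |

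- A vs B as sized: 373 + 144 = 517 in A and 517 in B, 1034 together.
- A vs C as sized: 144 + 246 = 390 in A and 212 + 246 = 458 in C, 848 together. This is the target of 847 with 491/2 = 245.5 rounded up. A vs D is the same.
- Overall: 517 + 517 + 2 × 212 + 3 × 246 = 2196 (section 13.1 gives 2195).

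**A vs B as section 13.6 reads.**

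- A becomes 763 against 517 in B, and 246/763 = 32% of the controls post-date arm B.
- Option 2 share: 390/763 = 51% in A against 146/517 = 28% in B. With concurrent controls only it is 144/517 = 28% in A, matching B.

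**How far the hazard ratio could move.** The documents give no FFS for the later patients, so this is an illustration. Assume no true effect of B, 5-year FFS of 80% in everyone except the 246 later controls, FFS of s in those 246, exponential times, 5 years of follow-up and no covariate adjustment. With λ = −ln(FFS)/5 and person-years per patient (1 − FFS)/λ:

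- s = 85%: control hazard = (517 × 0.20 + 246 × 0.15) / (517 × 4.481 + 246 × 4.615) = 140.3/3452 = 0.0406. The hazard for B is 0.0446, so the apparent HR is 1.10.
- s = 75%: (103.4 + 61.5) / (2316.9 + 1068.9) = 0.0487, so the apparent HR is 0.92.
- Over s from 70% to 87%, the HR runs from 0.84 to 1.14.

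**The secondary point.** If contemporaneously were taken as calendar time alone, up to 373/763 = 49% of the controls in A vs C or A vs D could come from Option 1. The sizing above excludes them: Appendix 4 ties the 144 to the four-way randomisation and heads its A vs C accrual table the same way.

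**The case against.** The strongest reply is that the protocol already shows the right sets. Section 13.2 treats recruitment to A vs B as something that is completed. Appendix 4 fixes A + B at 1034 and lists the later 246 arm A patients under the numbers needed for A vs C and A vs D. The reference to intention-to-treat can be read as analysis by allocated arm, not as an instruction to enlarge a finished comparison, and the SAP may say more. This stands as evidence of intent. It does not repair section 13.6, which sets the analysis population itself and names two of the three comparisons in its restriction.

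A second reply is that adjustment would absorb the difference. Centre, risk group and boost suitability are in the model and could remove part of an option difference. None of them addresses calendar period. Adjustment for pre-radiotherapy ADT duration is planned only in further adjusted models and is not a substitute.

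Three stronger readings are tempting and not supported:

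- A reader might infer that A vs C and A vs D are designed to include Option 1 controls. Sections 3 and 13.1 and Appendix 4 point the other way. Arms C and D recruited from the first half of 2018 to the end, so a calendar-only rule would exclude almost nobody, which makes that reading unlikely.
- A reader might infer that A vs B is biased in a known direction or loses a stated amount of power. The documents give no outcome by period or option, and the illustration moves either way.
- A reader might infer that the later controls are not randomised, or that arm B was stopped prematurely. They are randomised, though not against B, and B closed on reaching its target.

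**Conclusion.** The point holds for A vs B as a defect in the wording of section 13.6. Read literally, 32% of the A vs B controls (246 of 763) could not have been allocated to B, the option mix of the two arms differs (51% against 28% Option 2), and calendar period is not adjusted for. The counts are the protocol's own projections and will shift with actual recruitment. The effect on the hazard ratio is undetermined: the range of 0.84 to 1.14 under no true effect depends wholly on assumed FFS of 70% to 87% in the later controls and on no adjustment.

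For A vs C and A vs D the point is only that section 13.6 should state the control set that Appendix 4 already uses. The sample-size figures are not in question.

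**What to change.** In section 13.6, replace the sentence on controls with a rule for all three primary comparisons: each uses only patients randomised within an option and period in which both arms were open to them.

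- A vs B: Options 1 and 2 up to closure of arm B (517 vs 517).
- A vs C and A vs D: Option 2 patients only (about 390 vs 458 each).

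Stratify the Cox model by randomisation option and by allocation period (2:2:3:3, then 1:1:1). Once A vs B is limited as above, only the first period applies to it. For A vs C and A vs D, the period stratum also handles the change from 2:3 to 1:1 allocation. Carry the same definitions into the SAP before any unblinded comparison.

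The cost is wording only. The resulting sets match the 1034 and 847 already powered, so no patients are added and no planned power is lost.

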## 13. STATISTICAL CONSIDERATIONS

### 13.1. Statistical design and sample size

It is assumed that Failure Free Survival (FFS) at 5 years in the control arm (A) will be 80%. This estimate is based on unpublished data from high risk patients in CHHiP, which showed 5-year biochemical progression free rates of 84.4% [2]. Results from the M0 control cohort of the STAMPEDE trial [64] (a higher risk group than planned for PIVOTALboost), i.e. a FFS of 75% at 5 years in a subgroup of M0 N0 patients with planned RT (n=121) have also been considered.

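### FFS and the other cancer endpoints censor other-cause deaths yet are summarised by Kaplan-Meier, which modestly overstates the proportion of men who fail

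*Protocol*

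**What the plan says.** Section 13.3 of the protocol defines failure-free survival (FFS) as time from randomisation to the first of biochemical failure, "recommencement of androgen deprivation therapy, local recurrence, lymph node/pelvic recurrence, distant metastases or death due to prostate cancer". Death from any other cause is not an event.

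Section 13.4 treats the secondary endpoints as follows:
- Metastatic relapse free survival counts prostate cancer death only.
- Time to biochemical or clinical failure, time to loco-regional recurrence and time to recommencement of ADT count no deaths.
- Overall survival counts all deaths.
- For prostate cancer specific survival, and only there, the censoring rule is written out: "Patients dying from other causes will be censored at date of death".

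Section 13.6 then fixes the summary without separating these endpoints: "Time to event endpoints will be summarised presenting estimated Kaplan-Meier curves (by treatment"), and "the time point of primary interest is 5 years from randomisation, which will be presented with 95% CI for each treatment arm". For the comparison it says "Treatment effects will be estimated and tested for significance by the Cox proportional hazards model, adjusting by stratification factors".

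The updated calculation in section 13.1 requires 192 events for 80% power in A vs C (and in A vs D). It expects them when "847 patients, (822 plus 3% for loss to follow-up) are recruited over 6.5 years and followed up for 5 years". The Stata call in Appendix 4 shows no term for deaths from other causes.

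**The concern.** A man who dies of a heart attack before any failure can no longer fail. Censoring him and applying Kaplan-Meier treats him as if he had stayed at the same risk of failure as the men still being followed. One minus Kaplan-Meier then estimates failure in a hypothetical population in which nobody dies of anything else. It does not estimate the share of treated men who fail.

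What is at stake is the absolute figures: the 5-year rate in each arm, the absolute benefit of pelvic or boost radiotherapy, and any longer-term rates drawn from the 10 years of follow-up. Clinicians will read these as the chance of failing. The same omission affects planning, because men who die of other causes contribute fewer FFS events than the event calculation assumes.

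**Working it through.** **Inputs from the protocol**
- Control 5-year FFS 80%, hazard ratio 0.624, two-sided alpha 0.017, 1:1 allocation (section 13.1).
- 822 evaluable men, 847 with the 3% addition (822 × 1.03 = 846.7).
- 13 half-yearly accrual weights, and analysis at 23 half-years, that is 11.5 years (Appendix 4).

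**Assumption not in the protocol.** A constant, independent other-cause death hazard m of 1%, 2% or 3% per year, equal in both arms. The 80% is read as a net (Kaplan-Meier) figure.

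**Step 1: reproduce the plan.** The control hazard is λ = -ln(0.8)/5 = 0.0446 per year, and the experimental hazard is 0.624 × 0.0446 = 0.0278. With entry uniform within each half-year, expected events are 822 × the accrual-weighted mean of 1 - exp(-λf), averaged over the two arms, where f is time from entry to 11.5 years. With m = 0 this gives 192.0 events, exactly as stated. The requirement of 192 lies between the Schoenfeld (188) and Freedman (195) figures.

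**Step 2: Kaplan-Meier against cumulative incidence.**
1 - KM = 1 - exp(-λt). Cumulative incidence = λ/(λ+m) × [1 - exp(-(λ+m)t)].

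Example for arm A, 5 years, m = 0.02: 0.0446/0.0646 × (1 - exp(-0.323)) = 0.1907.

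| Failure probability | 1 - KM | m = 1% | m = 2% | m = 3% |
|---|---|---|---|---|
| Arm A, 5 years | 20.0% | 19.5% | 19.1% | 18.6% |
| Experimental arm, 5 years | 13.0% | 12.7% | 12.4% | 12.1% |
| Difference, 5 years (points) | 7.0 | 6.8 | 6.7 | 6.5 |
| Arm A, 10 years | 36.0% | 34.4% | 32.9% | 31.5% |
| Difference, 10 years (points) | 11.7 | 11.2 | 10.7 | 10.3 |

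In arm A the overstatement is 0.5, 0.9 and 1.4 points at 5 years, and 1.6, 3.1 and 4.6 points at 10 years. For scale, with the 517 arm A men of the A vs B comparison, the simple 5-year standard error is √(0.8 × 0.2/517) = 1.8 points. The 5-year bias is therefore about a quarter to three quarters of one standard error.

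**Step 3: events at 11.5 years with other-cause deaths.** Replace 1 - exp(-λf) by λ/(λ+m) × [1 - exp(-(λ+m)f)]. Power is Φ(½√d × |ln 0.624| - 2.387), where d is the number of events.

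| | m = 0 | 1% | 2% | 3% |
|---|---|---|---|---|
| Events from 822 men | 192.0 | 185.0 | 178.5 | 172.2 |
| Schoenfeld power | 81.1% | 79.4% | 77.7% | 76.1% |
| Events from 847 men, nobody otherwise lost | 197.8 | 190.7 | 183.9 | 177.5 |

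The loss is about 2 to 5 points of power. If the whole 3% addition is spent on deaths, 847 men still reach 192 events up to about 0.8% per year.

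**The case against.** **The analysis is coherent as written.** Kaplan-Meier with a Cox model that censors other-cause deaths is a consistent net analysis, and section 13.6 leaves further detail to a statistical analysis plan that is not shown and may add cumulative incidence. This stands in part. The hazard ratio is a valid cause-specific one, and a reader who inferred that the primary test is biased would go beyond the documents. But the estimator and the time point are not deferred: section 13.6 names both, and following them as written gives the overstated rates.

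**The bias is small where it is reported.** This stands. Five years is the stated time point, and there the bias is at most 1.4 points per arm under the assumed range. The larger 10-year figures matter only if 10-year rates are published. The protocol plans follow-up to 10 years but does not specify such estimates.

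**The sample size.** A reader might infer that 822 men cannot give 192 events. The documents do not support that. The figure reproduces exactly, and any shortfall rests on a mortality rate they do not supply. Section 1.1.11 does quote 5-year overall survival of 81-85%, but that is all-cause mortality in another trial, and this protocol excludes men with a life expectancy under 5 years. Section 13.1 also weighs source rates of 75% and 84.4% around the assumed 80%, an uncertainty that matters more for event numbers. Moreover, section 13.6 allows the principal analysis at a median follow-up of five years, which could come before the 11.5-year horizon, so an event count for that horizon should not become the plan's headline.

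**Explicit censoring.** The censoring sentence in section 13.4 belongs to prostate cancer specific survival. For FFS, censoring is inferred from the definition, although nothing in the text suggests any other handling.

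**Conclusion.** The point holds for the absolute failure rates. As section 13.6 is written, Kaplan-Meier estimates for FFS and the other endpoints that leave out some or all deaths will overstate the proportion of men who fail. Under an assumed 1-3% per year of other-cause deaths, constant, independent and equal between arms, the size is modest: 0.5-1.4 points in arm A at 5 years, with the 7.0-point difference becoming 6.8-6.5, and 1.6-4.6 points in arm A at 10 years if reported.

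Two stronger conclusions do not follow. The Cox test of the treatment effect is not invalidated, and the 192 events from 822 men is not an arithmetic error. That figure carries an unstated condition, namely no other-cause deaths. Relaxing it over the assumed range costs about 2 to 5 points of power at the 11.5-year horizon, and less if part of the 3% addition is free to absorb deaths.

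**What to change.** In section 13.6:
- State how other-cause deaths are handled for FFS.
- Keep the Cox model as the primary test, described as a cause-specific hazard ratio.
- Report failure rates per arm, and their differences, as Aalen-Johansen cumulative incidence.
- Treat other-cause death as the competing event for FFS, metastatic relapse and prostate cancer death.
- Treat any death as competing for biochemical or clinical failure, loco-regional recurrence and recommencement of ADT, since these count no deaths. A prostate cancer death without prior recorded failure competes here too.
- Label any Kaplan-Meier curve for these endpoints as a net estimate, and keep Kaplan-Meier for overall survival.

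In section 13.1 and Appendix 4, leave the stated 192 events and 847 patients as they are. At most, add a note that they assume no other-cause deaths, and that under an assumed 1-3% per year the same 822 men would give about 185-172 events at 11.5 years, roughly 2-5 points less power.

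The cost is a paragraph of analysis wording, one further estimator and an optional sentence on sample size. The survival endpoints in section 13.4 already require date and cause of death, so no patients, visits or procedures are added.
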